15.0 BIOSTATISTICS

15.1 Dose Escalation Study and Clinical Outcomes Analysis

The primary objective of this trial is to determine the maximum tolerated dose (MTD) of SBRT after at least 3 months of induction chemotherapy for patients with LAPC. Dose limiting toxicities (DLT) are defined by \geq Grade 3 treatment-related GI toxicity within 3 months of SBRT. These include: (1) Bowel (includes bowel perforation, obstruction, or hemorrhage) and (2) Stomach (bleeding ulcer, perforation). We will employ a modified 3+3 dose-escalation scheme.

Dose escalation will be evaluated after 3 evaluable patients who have completed 90 days of follow-up. Due to dropout during the 90-day follow-up period, up to 6 patients may be accrued at each dose level to yield a cohort of at least 3 evaluable patients. The dose level will be escalated if none of the evaluable patients followed for 90 days exhibits any DLT within 90 days of completion of SBRT. If a DLT is observed in one patient, an additional cohort of patients will be treated at that dose to achieve having at least 6 evaluable patients at that dose level. The dose will be escalated if none of the additional patients exhibits any DLT (i.e. at most 1 DLT is observed at that dose level). Dose-escalation stops and the previous dose will be considered the MTD if 2 or more patients have a DLT. If the previous dose level has been administered to fewer than 6 patients, an additional cohort of patients will be enrolled to achieve having at least 6 evaluable patients at that dose level. If at most 1 DLT is observed among all evaluable patients treated at that dose level, that dose level will be declared to be the maximum tolerated dose (MTD). If, however, there are a total of 2 or more DLTs, the dose will be de-escalated again. The MTD will be the greatest dose at which at least 6 evaluable patients are treated with at most 1 of them experiencing a DLT.

If 3 patients have completed the 90 day follow-up without a DLT and there have been more patients accrued at that dose level, the dose may be escalated based on 0 DLTs among the first 3 evaluable patients. However, if one of the additional patients treated at the lower dose subsequently experiences a DLT, the dose escalation will halt. At that point accrual will continue at the lower

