dose level to achieve a total of 6 evaluable patients who have completed the 90 day follow up at the lower dose; if at most 1 of all patients at that dose level experienced a DLT then dose escalation occur and accrual at the higher dose level will resume. If 2 or more patients have a DLT at that level, the previous dose will be considered the MTD (as described above).

For this design, the probability of escalation is as follows:

True toxicity rate	5%	10%	15%	20%	25%	30%	40%	50%
Probability of escalation	0.97	0.91	0.81	0.71	0.60	0.49	0.31	0.17

Dose escalation will start with dose level 1 (9 Gy x 3 fractions) and increase by 1 Gy per fraction at each dose level, dose level 2 will be 10 Gy x 3 fractions and dose level 3 will be 11 Gy x 3 fractions. The maximum number of patients needed for this dose escalation design is 18. A patient must be successfully treated according to prescription dose before he/she can be evaluated for the safety point, otherwise he/she will be replaced by a new patient. We expect to finish the enrollment (up to 18 patients) within 3 years. All toxicity profiles will be summarized and tabulated by dose level.

For the first secondary objective, the 2 year local control (LC) rate, progression free-survival (PFS), overall survival (OS) and patterns of failure for LAPC patients after induction chemotherapy and SBRT will be assessed using survival analysis tools such as Kaplan-Meier method or cumulative incidence curves if competing risks exist. To provide some simple comparison to the historical efficacy rates we will focus on OS due to its simplicity. The historical 2-year OS rate is approximately 20% and we expect to improve it to 40% by using the proposed treatment modality. Thus we expect that, out of the 22 patients at MTD level, we shall have at least 8 patients surviving beyond 2 years. Under the null hypothesis of 20%, the probability of observing at least 8 patients surviving beyond 2 years (i.e., type I error rate) is 5.6%. Due to the small sample size and lack of power, we will not use “at least 8 patients (out of 22) surviving beyond 2 years” as a formal decision rule for declaring the success of this study. The anticipation of at least 8 patients (out of 22) surviving beyond 2 years is merely to provide us a preliminary estimation of the efficacy signal relative to the historical control in this population.

For the above efficacy secondary objective, patients at different dose levels will be examined separately.

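### Section 15.1 gives 18 both as the most patients the design can need and as the enrolment figure, but 3 levels x 6 = 18 counts DLT-evaluable patients only and leaves no room for the losses the plan expects

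*Combined protocol and SAP*

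**What the plan says.** Section 15.1 gives the study size twice within three sentences: "The maximum number of patients needed for this dose escalation design is 18" and "We expect to finish the enrollment (up to 18 patients) within 3 years". Section 4.1 describes a study of at most 18 patients, section 1.0 anticipates that number accrued, and section 7.0 gives it as the accrual target.

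The escalation rules in the same section count evaluable patients. After one DLT in the first cohort, "an additional cohort of patients will be treated at that dose to achieve having at least 6 evaluable patients at that dose level". At the end, "The MTD will be the greatest dose at which at least 6 evaluable patients are treated", with no more than one of them having a DLT.

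Losses are provided for in two places:

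- For dropout during the 90 days, "up to 6 patients may be accrued at each dose level to yield a cohort of at least 3 evaluable patients".
- Between the two statements of 18, a patient must have received the prescribed treatment to count for safety, "otherwise he/she will be replaced by a new patient".

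No loss rate is stated. No accrual number is given for a level that has to reach 6 evaluable.

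**The concern.** A maximum that holds only when nobody is lost is not a maximum for enrolment. If all three levels are expanded, the design uses 18 evaluable patients, and the first dropout or replacement makes the next patient the 19th enrolled.

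What follows depends on a point the documents leave open. If 18 enrolled is applied as a limit, the trial can run out of patients before its own MTD definition can be applied, and the MTD is the primary objective. If it is not a limit, 18 understates the enrolment that the approving bodies and the site should plan for, and no ceiling is stated.

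**Working it through.** **Inputs from the plan.** Three dose levels; 3 evaluable in the first cohort; 6 evaluable after one DLT, and 6 at the declared MTD; stated size 18; 10-15 eligible patients per year for 3 years (section 7.0).

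**Inputs assumed, because the plan gives none.** Loss rates of 5%, 10% and 20%, independent of DLT, and the five sets of DLT rates in the table below.

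**Step 1: the plan's figure.** 3 x 6 = 18, so the stated number is reproduced as a count of evaluable patients with zero losses and no level above 6.

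**Step 2: the rules are the sponsor's.** With DLT rate p, the probability of escalating is (1-p)^3 + 3p(1-p)^2 x (1-p)^3. At p = 0.10 this is 0.729 + 0.177 = 0.906, against 0.91 in the plan's table. All eight entries of that table are reproduced.

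**Step 3: the chance of no loss among 18.** (1-d)^18 is 0.397 at 5% loss, 0.150 at 10% and 0.018 at 20%. If all 18 evaluable are needed, 18 accruals therefore fall short with probability 0.603, 0.850 and 0.982.

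**Step 4: how often this bites.** Let E be the number of evaluable patients the rules require. I enumerated E exactly, holding a level with no DLT in its first cohort at 3 evaluable and filling the declared MTD level to 6. Then

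P(more than N accruals) = sum over e of P(E = e) x P(Binomial(N, 1-d) < e).

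Worked case, DLT rates 0.10, 0.20, 0.30, with d = 0.10 and N = 18. P(E = 12, 15, 18) = 0.430, 0.308, 0.074, and the chances that 18 accruals are too few are 0.0012, 0.098 and 0.850. The sum is 0.0005 + 0.030 + 0.063 = 0.094.

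| DLT rates by level | Mean E | P(E = 18) | P(>18 accruals), 5% loss | 10% loss | 20% loss |
|---|---|---|---|---|---|
| 0.05, 0.10, 0.15 | 12.90 | 0.036 | 0.025 | 0.062 | 0.223 |
| 0.10, 0.15, 0.20 | 12.54 | 0.064 | 0.042 | 0.087 | 0.247 |
| 0.15, 0.20, 0.30 | 11.76 | 0.080 | 0.051 | 0.096 | 0.236 |
| 0.10, 0.20, 0.30 | 12.44 | 0.074 | 0.048 | 0.094 | 0.249 |
| 0.17, 0.17, 0.17 | 11.40 | 0.065 | 0.042 | 0.081 | 0.214 |

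Twelve or fewer evaluable patients suffice in 61.5-67.3% of trials, so most trials have room for losses within 18.

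**Step 5: illustrative ceilings, same formula.** At 10% loss, N = 20 leaves the rules incomplete in 1.5-2.9% of trials and N = 22 in 0.3-0.5%. At 20% loss, N = 24 leaves 1.1-1.9% incomplete.

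**The case against.** The best defence is that nothing is miscalculated. 3 x 6 = 18 is right, and the replacement sentence comes directly after the statement of the maximum. A fair reader can take 18 as the patients the design needs, with replacements on top. That replacement rule applies at every level and has no cap, and the expansion rule fills to 6 evaluable without an accrual ceiling. Sections 1.0 and 7.0, and the enrolment sentence in 15.1, word 18 as an anticipation, target or expectation; only section 4.1 puts it flatly.

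Much of this stands, and it limits the point in three ways.

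- A reader might infer that 18 is a hard cap and that the rules therefore contradict it outright. No passage says so; this is an ambiguity about what 18 counts.
- A reader might infer that 6 accrued is a ceiling at every level, so that one loss defeats any expanded level. The allowance is written for obtaining at least 3 evaluable and sets no limit for reaching 6.
- A reader might assume that every first cohort is filled to 6, which would make overruns much more frequent. The plan permits that number because of dropout, not as routine. Target accrual of 18 over 3 years is about 1.5 patients per 90 days, which makes it unlikely.

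What the defence does not remove is that no enrolment figure including losses appears anywhere. If replacements come on top of 18, then describing enrolment as at most 18 is wrong. Nor is it clear who counts: section 5.1 places enrolment before fiducial placement, while section 9.1 lists fiducial placement under screening.

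**Conclusion.** The point holds as an unclear and, for enrolment, understated study size. Eighteen is the largest number of DLT-evaluable patients the rules require if no level exceeds 6. It is not the largest number that may have to be enrolled.

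The consequence is modest. More than 18 accruals are needed in at most about one trial in ten at losses of 5-10%, and in about one in four or five at 20%. Every one of these figures rests on assumed DLT and loss rates, and on clean levels staying at 3 evaluable. The plan also allows that "the dose may be escalated based on 0 DLTs among the first 3 evaluable patients" when more patients have already been accrued at that level, so a clean level can use more than 3. The figures are therefore towards the low end.

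A separate inconsistency should be settled in the same edit. The overall-survival illustration in 15.1 speaks of survivors "out of the 22 patients at MTD level", and 22 exceeds the whole-trial 18. A reader might take that as evidence that a larger trial was intended. The documents do not say so, and the point above does not depend on it.

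**What to change.** In section 15.1, replace the statement of the maximum with wording such as: *The rules require no more than 18 DLT-evaluable patients (three levels of six), provided no level exceeds six. Non-evaluable patients are replaced. Total enrolment, replacements included, will not exceed N.* Derive N from one stated loss rate, and give the accrual allowed at a level that must reach 6 evaluable. At 10% loss, N = 20 would be a reasonable illustration.

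Alternatively, keep 18 enrolled as a cap, drop the claim that it is the most the design can need, and state the probability that the rules are not completed (6.2-9.6% at 10% loss under the assumptions above).

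Either way, define who counts towards the total, say what will be concluded if the limit is reached without an MTD, and align sections 1.0, 4.1 and 7.0. Separately, reconcile the 22 in the survival illustration with the trial size; a total enrolment ceiling must not be read as that 22.

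The cost is wording in four sections and a ceiling a few patients higher. Expected accrual at 10% loss is mean E / 0.9, that is 11.40/0.9 = 12.7 to 12.90/0.9 = 14.3, so few patients beyond 18 are likely. A ceiling of 20 is 20/45 = 44% to 20/30 = 67% of the 30-45 eligible patients implied over 3 years, against 40-60% for 18. No dose, DLT definition or escalation rule changes.

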14.0 CRITERIA FOR REMOVAL FROM STUDY

- Development of an intercurrent medical condition or need for concomitant treatment that precludes further participation in the trial
- Unacceptable toxicity or any adverse event that precludes further participation in the trial
- Patient is not treated according to the prescription dose
- The investigator removes the patient from the trial in the best interests of the patient
- Patient death
- Study completion or discontinuation
- Patient withdraws consent to continued participation in the trial or is lost to follow-up

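### The replacement rule has no exception for a patient whose DLT is the reason treatment or follow-up was not completed, so a DLT can drop out of the escalation and MTD counts

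*Combined protocol and SAP*

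**What the plan says.** Section 15.1 sets the condition for entering the safety evaluation: a patient "must be successfully treated according to prescription dose before he/she can be evaluated for the safety point, otherwise he/she will be replaced". Section 14 lists among its removal criteria "Patient is not treated according to the prescription dose" and, separately, "Unacceptable toxicity or any adverse event that precludes further participation in the trial". Neither section says what happens to a DLT that was itself the reason for stopping.

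The plan never formally defines evaluable. Two working conditions can be read from section 15.1: treated to the prescribed dose, and followed for 90 days.

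The counting rules in section 15.1 use different populations:

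- Escalation after the first cohort requires that "none of the evaluable patients followed for 90 days exhibits any DLT within 90 days of completion of SBRT".
- The MTD is the highest dose where "at least 6 evaluable patients are treated with at most 1 of them experiencing a DLT".
- Expansion: "If a DLT is observed in one patient, an additional cohort of patients will be treated at that dose".
- Stopping: "the previous dose will be considered the MTD if 2 or more patients have a DLT".
- Resumption, after a late DLT at a lower level has halted escalation: "if at most 1 of all patients at that dose level experienced a DLT".

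The DLT definition in sections 13.1 and 15.1 gives a window of 3 months from SBRT, without saying whether it starts at the first or the last fraction. The escalation rule dates its 90 days from completion of SBRT.

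**The concern.** SBRT is given in three fractions on alternate days (section 4.2), so a grade 3 or higher GI toxicity can arise before the course is finished. On the literal text that patient was not treated to prescription, cannot be evaluated for safety, and is replaced. The event that the trial exists to count would then be the reason for not counting it.

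There is a second route. A patient may complete SBRT, have a DLT, and then die or withdraw before day 90. That patient does not meet the 90-day follow-up condition either. The DLT definition includes perforation and hemorrhage, so this route cannot be ignored.

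At stake is the primary decision rule. With three to six patients per level, one DLT separates escalation from expansion, or a qualifying dose from a failed one. As written, the team would have to settle how to count the event after seeing it, while deciding whether to treat the next patients at a higher dose.

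**Working it through.** **The rules side by side.** Apply each rule to the same data.

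| Data at one dose level | Rules counting evaluable patients | Rules counting patients or all patients |
|---|---|---|
| 3 evaluable, no DLT; 1 further patient stopped SBRT with a DLT and was replaced | 0 DLTs: escalate | 1 DLT: expand |
| 6 evaluable, 1 DLT; 1 further patient stopped SBRT with a DLT and was replaced | 1 of 6: qualifies as MTD | 2 DLTs: level fails |

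If patients is shorthand for evaluable patients, the right-hand column collapses into the left, and every rule omits the event.

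**The window.** For a patient who never completes SBRT, 90 days from completion has no starting date, so the escalation rule cannot be applied to that patient at all.

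**The plan's own figures.** With true DLT rate p, the 3+3 formula is P(escalate) = (1-p)^3 + 3p(1-p)^5. At p = 5, 10, 15, 20, 25, 30, 40 and 50% it gives 0.973, 0.906, 0.814, 0.709, 0.600, 0.494, 0.309 and 0.172. These match all eight entries of the section 15.1 table (0.97 to 0.17).

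**Average effect if such DLTs are dropped.** Let f be the share of DLTs that interrupt SBRT. The documents do not give f. Assume uniform onset. Three alternate-day fractions span 4 days from first to third, or 5 calendar days, so f = 4/94 = 0.043 to 5/95 = 0.053; take about 0.05.

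- Replacement without limit: the DLT rate among evaluable patients is q = p(1-f)/(1-pf). At p = 0.30 and f = 0.05, q = 0.285/0.985 = 0.289, and (1-q)^3 + 3q(1-q)^5 = 0.359 + 0.157 = 0.516.
- Strict cap of 6 accrued per level: P = (1-p)^3 × [1 + 3pf + 6(pf)^2 + 10(pf)^3] + 3p(1-f)(1-p)^5. At the same values, 0.343 × 1.0464 + 3 × 0.285 × 0.168 = 0.359 + 0.144 = 0.503.

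| True rate p | Table value (f = 0) | f = 0.05, cap / no cap | f = 0.10, cap / no cap |
|---|---|---|---|
| 20% | 0.709 | 0.714 / 0.726 | 0.721 / 0.744 |
| 30% | 0.494 | 0.503 / 0.516 | 0.512 / 0.539 |
| 40% | 0.309 | 0.318 / 0.330 | 0.328 / 0.351 |

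At f = 4/94 and p = 0.30 the pair is 0.501 / 0.513. At f = 0.20, without a cap, it would be 0.588.

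**How often a first cohort is affected.** P(at least one of the first 3) = 1-(1-pf)^3. At f = 0.05 this is 0.030, 0.044 and 0.059 for p = 20, 30 and 40%.

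**Effect once it happens.** Suppose one first-cohort patient stops SBRT with a DLT, the others are independent, and none of them is replaced.

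| Reading | Formula | p = 20% | p = 30% | p = 40% |
|---|---|---|---|---|
| DLT counts, patient not replaced | (1-p)^5 | 0.33 | 0.17 | 0.08 |
| DLT dropped, cap of 6 | (1-p)^3 | 0.51 | 0.34 | 0.22 |
| DLT dropped, no cap | (1-p)^3 + 3p(1-p)^5 | 0.71 | 0.49 | 0.31 |

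Section 15.1 states the limit of 6 only for reaching 3 evaluable patients. Applying it to the expanded cohort is an assumption, made plausible by the total of 18 over three levels.

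**The case against.** The strongest case against has four parts.

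- **Any sensible team would count the event.** Probably so. But the sentence as written says otherwise, and a rule for the primary endpoint should not need to be overridden after the fact.
- **The event would not be hidden.** This stands. Section 15.1 tabulates all toxicity by dose level. A serious event reaches the DSMC within 5 business days, and the DSMC can suspend or close the trial (section 17.1). But no text says how the event enters the count.
- **The rules may not contradict each other.** Section 15.1 elsewhere uses patients and evaluable patients interchangeably, so the broader terms may be shorthand. This is a fair reading. It removes the contradiction, but at the price of dropping the DLT everywhere.
- **The prescription-dose condition has a legitimate purpose.** This also stands. A patient treated off-prescription for reasons unrelated to toxicity says little about the assigned level. The fix should keep that purpose.

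Three stronger inferences are tempting, and the documents do not support them. A reader might take the escalation table as proof that every DLT was meant to count. It is the 3+3 formula at a stated true toxicity rate with no denominator given, so it supports neither reading and is not in error. A reader might infer from section 14 that the data of removed patients are discarded; it only lists reasons for leaving the study. A reader might also infer that the MTD will be materially too high on average; the working shows a small expected shift.

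**Conclusion.** The gap is real. Followed literally, the replacement sentence makes a patient whose DLT interrupts SBRT non-evaluable, and the zero-DLT and MTD rules then leave that DLT out. The same holds for a DLT followed by death or withdrawal before day 90.

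The expected effect of the interruption route is probably small: a rise of about 0.01-0.02 in the chance of escalating at a true 30% rate, with roughly a 4% chance that a first cohort is affected. Both figures rest on the assumed f of about 0.05 from uniform onset. The follow-up route cannot be sized from the documents. Conditional on the event, the choice of reading changes the chance of escalation at least twofold at a 30% rate.

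It should be fixed before any cohort decision. A stated rule can produce a wrong escalation or MTD decision, and the remedy is a few sentences. The escalation table needs no change.

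**What to change.** Reconcile sections 13.1, 14 and 15.1 around one definition of DLT-evaluable, and use it in every escalation, expansion, stopping, resumption and MTD count:

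- A patient who has received at least one fraction at the assigned dose level and has a DLT is DLT-evaluable and is not replaced, even if that toxicity prevented completion of SBRT or of the 90-day follow-up.
- Only patients without a DLT who are incompletely treated, or not followed for 90 days, are replaced.
- Patients treated off-prescription for reasons unrelated to toxicity are handled by a separate rule fixed in advance, and any DLT they have is still reported.
- One DLT window applies throughout, from the first fraction to 90 days after the last fraction received.

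Section 14 should cross-refer to this definition, so that removal from study is not read as removal from the DLT count.

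The cost is a few sentences and, by design, no extra patients. The downside is that escalation becomes slightly more conservative than on the reading that drops the DLT.

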1.0 PROTOCOL SUMMARY AND SCHEMA

This is a dose escalation trial to evaluate the safety of stereotactic body radiotherapy (SBRT) delivered in 3 fractions for patients with locally advanced pancreatic cancer (LAPC) who have received induction chemotherapy (FOLFIRINOX or gemcitabine and nab-paclitaxel). The primary objective is to determine the maximum tolerated dose (MTD) of 3-fraction SBRT for patients with LAPC. We will develop and implement functional imaging methods to evaluate post-SBRT effects on normal tissue and tumor cellularity and perfusion/permeability that may provide quantitative biomarkers of tumor response as well as early indicators of bowel toxicity. We anticipate (up to) 18 patients to be accrued over 3 years.

SCHEMA

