4.0 OVERVIEW OF STUDY DESIGN/INTERVENTION

4.1 Design

This is a phase I study of up to 18 patients to identify the maximum tolerated dose (MTD) of a 3-fraction regimen of SBRT for locally-advanced pancreatic cancer patients who have not developed distant progression following induction chemotherapy (FOLFIRINOX or gemcitabine and nab-paclitaxel as per standard of care). Using pCT to quantify tissue perfusion/permeability and associated heterogeneity after SBRT, we will define early normal tissue changes associated with GI toxicity requiring early interventions as well as tumor changes associated with local control or progression that can dictate further therapy choices for patients with LAPC.

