7.0 RECRUITMENT PLAN

This study will be available to all patients seen at University of Colorado who meet the eligibility criteria. University of Colorado is a referral center for pancreatic cancer and all patients considered for this study will be presented at a weekly multidisciplinary Pancreatic Multidisciplinary Conference. In addition, the study will be placed on the University of Colorado Website to maximize patient recruitment. Patients will be identified from surgical, gastroenterology and medical oncology clinics for treatment of their disease. The investigators take due notice of the NIH policy concerning inclusion of women and minorities in clinical research populations.

Patient recruitment will continue for a period of 3 years. Based on past census values at University of Colorado, we expect 10-15 local pancreatic cancer patients will be eligible for this study per year. The target accrual is 18 patients over 3 years.

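### The 2-year survival benchmark assumes 22 patients at the MTD, but the whole trial enrols at most 18 across three dose levels

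*Combined protocol and SAP*

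**What the plan says.** Section 15.1 takes a historical 2-year overall survival rate of about 20% and hopes for 40%. It then says: "Thus we expect that, out of the 22 patients at MTD level, we shall have at least 8 patients surviving beyond 2 years". Under the 20% rate it gives the chance of 8 or more survivors as 5.6% and labels this the type I error rate. It adds that the count is not a formal decision rule and is "merely to provide us a preliminary estimation of the efficacy signal relative to the historical control in this population".

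On the size of the trial, the same section says: "The maximum number of patients needed for this dose escalation design is 18". Other sections agree:
- Section 1.0: "We anticipate (up to) 18 patients to be accrued over 3 years"
- Section 4.1: "This is a phase I study of up to 18 patients"
- Section 7.0: "The target accrual is 18 patients over 3 years"

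Section 15.1 names three dose levels. On the number needed at the chosen dose it says: "The MTD will be the greatest dose at which at least 6 evaluable patients are treated", with at most one dose-limiting toxicity among them. On how survival is to be analysed it says: "For the above efficacy secondary objective, patients at different dose levels will be examined separately".

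**The concern.** A single dose level cannot hold 22 patients when all three levels together hold at most 18. The figure does not look like a typing slip, because 22 recurs through the paragraph and the 5.6% was evidently computed from it. It may come from an expansion cohort, but the available text describes none.

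The benchmark is the plan's only numerical comparison of efficacy with the historical rate. If its denominator cannot occur, neither the expected count nor the error rate describes this trial. A treatment that truly achieved 40% could fall short of 8 survivors through sample size alone and be read as showing no signal. A reader also cannot tell whether 18 patients are planned or a larger number.

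**Working it through.** **Inputs, all from section 15.1 unless noted**
- Null and hoped-for 2-year survival: 20% and 40%.
- Benchmark: at least 8 of 22 at the MTD; stated type I error 5.6%.
- Total enrolment: up to 18 (also sections 1.0, 4.1 and 7.0).
- Dose levels: three. Patients required at the MTD: at least 6 evaluable.

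**1. Reproduce the plan's figure.** With X ~ Binomial(n, p), P(X ≥ 8) is the sum over k = 8 to n of C(n, k) p^k (1 − p)^(n − k).
- n = 22, p = 0.20: 0.0561, which matches the stated 5.6%.
- n = 22, p = 0.40: 0.710.
- Neighbouring sizes at p = 0.20: n = 21 gives 0.043 and n = 23 gives 0.072.

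With a threshold of 8 the printed 5.6% therefore belongs to n = 22 and to no other size.

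**2. How many patients can the MTD level hold?** Three levels of 6 make 3 × 6 = 18, which agrees with the stated maximum. A level can exceed 6 through replacement or continued accrual while follow-up matures. For an upper bound, assume at least 3 patients on every other level used (the reviewer's assumption):
- MTD = level 1, with level 2 also opened: 18 − 3 = 15.
- MTD = level 2 or 3, with all levels opened: 18 − 6 = 12.

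On the same assumption, 22 at the MTD would need a total of 22 + 3 = 25 or 22 + 6 = 28 patients, which is 7 to 10 above the cap.

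**3. Apply the literal benchmark of 8 survivors to those sizes**

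| n | P(X ≥ 8), p = 0.20 | P(X ≥ 8), p = 0.40 |
|---|---|---|
| 6 or 7 | 0 | 0 |
| 12 | 0.0006 | 0.057 |
| 15 | 0.0042 | 0.213 |
| 18 (all levels pooled) | 0.016 | 0.437 |
| 22 (as stated) | 0.056 | 0.710 |

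**4. What could 6 patients show?** Expected survivors are 6 × 0.20 = 1.2 or 6 × 0.40 = 2.4. A count of at least 3 of 6 has probability 0.099 under 20% and 0.456 under 40%. With complete follow-up, 2 survivors of 6 have an exact (Clopper-Pearson) 95% interval of 4% to 78%, which covers both rates.

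**5. Could another source supply the 22?**
- Pooling dose levels gives at most 18, and the plan rules pooling out for this objective.
- Section 18.0 mentions combining data with a similar study at another centre for publication. It gives no number, section 15.1 does not refer to it, and the text places the 22 at the MTD level.

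**The case against.** The strongest reply is that little depends on the number. Section 15.1 itself cites small sample size and lack of power, declines to use the count as a decision rule, and triggers no action from it. Someone with about 6 patients at the MTD would probably see that 8 of 22 cannot apply. This stands as a limit on severity, but it does not make the figures right. The disclaimer about small numbers was written for 22 patients and does not warn that the real number may be nearer 6.

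A second point is that holding the count at 8 while n shrinks overstates the loss of information. With a threshold near the same proportion (8/22 = 36%), at least 5 of 12 has 7.3% type I error and a 56% chance under 40%; at least 6 of 15 has 6.1% and 60%. This is fair. The fixed-count rows show that the text fails as written; they do not measure how much could be learned with a rescaled threshold.

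Third, the ceilings of 12 and 15 rest on an assumption, and it is not stated whether 18 counts enrolled or evaluable patients. The wording also varies: section 1.0 anticipates 18 and section 7.0 targets it, whereas sections 4.1 and 15.1 state it as a maximum. None of these readings puts 22 patients at one dose level.

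**Conclusion.** The concern holds. The 5.6% is correctly computed for a sample that exceeds the entire trial by 22 − 18 = 4 patients and is more than three times the 6 required at the MTD. At 6 patients the benchmark cannot be met even if everyone survives.

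The contradiction needs no assumption; it follows from the stated totals. Only the ceilings of 12 and 15, and the implied totals of 25 to 28, depend on assuming at least 3 patients on each other level used. All the survival probabilities assume complete 2-year follow-up.

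The consequence is confined to the interpretation of a secondary, descriptive comparison. The escalation rules, the MTD determination, the safety summaries and the planned Kaplan-Meier estimates are unaffected. It should be fixed because the stated sample size and error rate are wrong as written and the correction is easy.

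**What to change.** **Preferred.** Remove the 22, 8 and 5.6% figures from section 15.1 and replace them with a statement such as:

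> Up to 18 patients will be enrolled in total; the MTD requires at least 6 patients evaluable for dose-limiting toxicity. Two-year overall survival will be reported by dose level as the Kaplan-Meier estimate with its 95% confidence interval. No benchmark count applies.

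Evaluability for dose-limiting toxicity is a 90-day criterion, so the text should not imply that 6 patients will have 2-year survival status. Giving the 4% to 78% interval for 2 of 6 would show readers the precision to expect. This rewords one paragraph and needs no extra patients; the only cost is a less favourable stated expectation.

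**If 22 was intended.** State in section 15.1 whether it comes from an expansion cohort or from the combined dataset mentioned in section 18.0, describe that cohort or pooled analysis, and make the totals in sections 1.0, 4.1, 7.0 and 15.1 agree with it. This costs either accrual above 18 or a defined external dataset.

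**If a pooled benchmark is wanted.** At least 7 of 18 has 5.1% type I error under 20% and a 63% chance under 40%, given complete 2-year follow-up. It mixes dose levels, so the sentence on examining them separately would have to change. That is a design choice and is not needed to correct the error.
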